9.6.5.1 Primary Efficacy Analysis: Carotid Artery IMT Analyses

The primary end point will be the per-subject rate of change in the right distal CCA far wall IMT. The rate of change in the right distal CCA far wall CIMT will be computed for each participant by fitting a regression line of CIMT on years since baseline ultrasound. The estimated slope of the regression line will be used as that subject's CIMT rate of change. Analyses of trial end points will be performed on the intent-to-treat sample, which will be defined as all randomized participants who had a baseline and at least 1 follow-up CIMT measurement taken after randomization.

The statistical approach outlined above will be accomplished using mixed effects models for longitudinal data, with the randomization stratification variable (dichotomized baseline CIMT) used as a covariate. Each CIMT measure will be included as a dependent variable. The regression coefficient associated with the model covariate of time on-study will estimate the average group progression rate of CIMT (in mm/year). Random effects terms for the regression intercept and slope (change over time) will allow for individual participant deviations from their group average in baseline CIMT and CIMT rate of change, respectively. The statistical test for differences in the CIMT rate by treatment group will be accomplished by adding a treatment group by time on-study interaction term. The significance of the regression coefficient associated with this interaction term is the test that the CIMT rates differ by treatment group. We will also evaluate baseline plasma levels of insulin, lipids/CRP, hemoglobin A1c, coagulation factors, rheology parameters and inflammatory variables, dietary nutrients, smoking, blood pressure, physical activity and use of non-study medications as potential confounders. If any of these variables are found to be confounders of treatment-rate of CIMT relationship, they will be included as

covariates in the analysis.

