9.6.7 Ancillary Statistical Analyses

9.6.7.1 Within-Group Analyses

The effects of on-trial end point variables other than treatment modality on the per-subject rate of change in CIMT, arterial stiffness and cognition will be separately assessed. The parameters to be tested will include laboratory data (plasma insulin, lipids/CRP, hemoglobin A1c, coagulation factors, rheology parameters, inflammatory variables and nattokinase levels), clinical variables (blood pressure, body mass, waist:hip ratio, etc.), and lifestyle variables (dietary intake, physical activity, smoking, etc.). Baseline and on-trial values of these data will be collected in order to address questions of clinical significance within each treatment group such as: 1) which baseline characteristics have differential effectiveness on the rate of change in CIMT; and, 2) what is the role of changes in these variables on the rate of change in CIMT. These analyses will utilize mixed effects models and generalizing estimating equations with CIMT (arterial stiffness, cognition) as the dependent variable. Analyses will be conducted in the combined sample with a covariate included to control for treatment group. Interaction terms with treatment group will be introduced to test whether relationships between independent variables and the trial end point are of equal magnitude between the 2 study groups. Experiment-wise error rates in these analyses will be controlled. All participants contributing at least one follow-up ultrasound (or cognitive test) will be included in these analyses.

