9.6.7.2 Modifiers of Treatment Efficacy

The extent to which treatment effects are modified by other subject-specific factors will be examined. Potential treatment effect modifiers include baseline CIMT, smoking status (on-trial smokers versus non-smokers), BMI, age and gender. The statistical significance of differences in the treatment effect by subgroup will be tested by inclusion of an interaction term (treatment by subgroup) in the efficacy models detailed above. For descriptive comparisons, treatment effect sizes will be computed for each level of the possible modifier.

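### For CIMT and stiffness, the effect-modifier test in 9.6.7.2 names a treatment-by-subgroup term, which in the stated mixed model compares levels and not rates of progression

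*Combined protocol and SAP*

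**What the plan says.** Section 9.6.7.2 lists baseline CIMT, on-trial smoking, BMI, age and gender as possible modifiers. Its target is "The statistical significance of differences in the treatment effect by subgroup", and the test "will be tested by inclusion of an interaction term (treatment by subgroup) in the efficacy models detailed above". No time term is named. It also plans descriptive effect sizes at each level of the modifier.

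The CIMT model is in 9.6.5.1. "The primary end point will be the per-subject rate of change in the right distal CCA far wall IMT", obtained by "fitting a regression line of CIMT on years since baseline ultrasound". The section then says that this approach is carried out with mixed effects models, in which "Each CIMT measure will be included as a dependent variable". There are random intercepts and slopes, and a treatment-by-time term is added: "The significance of the regression coefficient associated with this interaction term is the test that the CIMT rates differ by treatment group".

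Section 9.6.5.2 applies the same methods to stiffness. Section 9.6.5.3 analyses cognition as change from baseline, with treatment group itself as the effect.

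In 9.6.7.1, CIMT (or stiffness, or cognition) is again the dependent variable, and "Interaction terms with treatment group will be introduced to test whether relationships between independent variables and the trial end point are of equal magnitude".

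**The concern.** The term that 9.6.7.2 names matches the treatment effect only when the outcome is already a change or a slope. In a model of repeated CIMT values with time measured from baseline, treatment by subgroup asks whether the arms differ in level by a different amount in each subgroup. For a modifier fixed at baseline, randomization puts the true value of that contrast at zero when treatment starts. Whether nattokinase slows progression more in one subgroup is carried by treatment by time by subgroup, which is not named.

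An analyst who follows the sentence would usually find nothing and could report a uniform effect on progression that had not been tested. If the term did reach significance, it would be in mm rather than mm/yr and could point the wrong way.

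**Working it through.** The documents supplied give no power, effect size or variance for this analysis, so there is no figure to reproduce. The check compares the literal term with the three-way term under the same true difference.

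**Inputs from the plan**
- 240 participants (1.3). With 1:1 allocation (assumed) and a 50/50 split, as targeted for gender in 3.1, there are 240/4 = 60 per cell.
- Two baseline scans and six on-trial scans at six-month intervals (9.3.3). Both baseline scans are placed at time 0, so times are 0, 0, 0.5, ..., 3 years.
- Coefficient of variation below 3% (8.3.2). Residual SD = 0.03 × 0.75 mm = 0.0225 mm; taking 0.75 mm as the typical CIMT is an assumption.

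**Assumed, not in the plan**
- Intercept SD 0.12 mm; slope SD s = 0.010-0.020 mm/yr; intercept-slope correlation r from -0.5 to +0.5.
- True subgroup difference in the treatment effect δ = 0.012 mm/yr; no dropout; two-sided α = 0.05, since 9.6.7.2 states none.

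**Variance of a participant's fitted intercept and slope.** Mean time is 1.3125 years and the sum of squares about it is 8.969. Residual variance is 0.0225² = 0.000506.
- V11 = 0.12² + 0.000506 × (1/8 + 1.3125²/8.969) = 0.01456
- V12 = r × 0.12 × s - 0.000506 × 1.3125/8.969 = 0.12rs - 0.0000741
- V22 = s² + 0.000506/8.969 = s² + 0.0000564
- ρ = V12/√(V11 × V22)

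**Three-way term.** SE = √(4 × V22/60), λ₃ = δ/SE, and power = Φ(λ₃ - 1.96) + Φ(-λ₃ - 1.96).
- s = 0.010: SE 0.00323, λ₃ = 3.72, power 96%
- s = 0.015: SE 0.00433, λ₃ = 2.77, power 79%
- s = 0.020: SE 0.00552, λ₃ = 2.18, power 59%

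**Literal term, with the three-way term left out.** Its expected value is -(V12/V22) × δ and its SE is √(4 × V11 × (1 - ρ²)/60). Hence λ = λ₃ × |ρ|/√(1 - ρ²), with the same power formula.

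| Slope SD (mm/yr) | Three-way | Literal, r = -0.5 | r = -0.3 | r = 0 | r = +0.3 | r = +0.5 |
|---|---|---|---|---|---|---|
| 0.010 | 96% | 46% | 20% | 5.4% | 11% | 28% |
| 0.015 | 79% | 33% | 14% | 5.1% | 10% | 24% |
| 0.020 | 59% | 24% | 11% | 5.0% | 9% | 18% |

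**Sign.** At s = 0.015 and a true difference of +0.012 mm/yr:
- r = -0.3: V12 = -0.000614, expected estimate = (0.000614/0.0002814) × 0.012 = +0.026 mm
- r = +0.3: V12 = +0.000466, expected estimate = -(0.000466/0.0002814) × 0.012 = -0.020 mm

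The same true difference gives opposite signs. The extra power away from r = 0 is leakage from the omitted term, not a test of progression.

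**Simulation (s = 0.015).** Mixed-model fits rejected in 26 of 462 data sets (5.6%) for the literal term at r = 0, against about 82% for the three-way term. With no true difference, the literal term rejected in 5.2% of 250 runs. At r = -0.3 and +0.3 the literal term gave 9.3% and 7.9%, somewhat below the formula's 14% and 10%. A larger check on per-subject intercepts and slopes (1,500 data sets each) gave 14% and 12%. Treatment by subgroup in a regression of per-subject slopes had 77-84% power, the same as the three-way term (77-83%).

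**The case against.** The strongest reply is that the parenthesis is shorthand. One sentence covers CIMT, stiffness and cognition, and its stated target is a difference in the treatment effect. For CIMT that effect is treatment by time, so its difference by subgroup is the three-way term. The planned effect sizes at each level of the modifier fit this reading, because a model with a common treatment-by-time term could not supply them. Section 9.6.5.1 also defines the end point as a per-subject slope, and 9.6.7.3 uses annualized rates as outcomes; with such an outcome treatment by subgroup is the correct term.

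Much of this stands: the sponsor may well intend the right test. It does not settle what will be run. Section 9.6.5.1 says that the slope approach is implemented as a mixed model of CIMT values, and that is the efficacy model to which 9.6.7.2 refers. Section 9.6.7.4, with the same level outcome, names its interaction with time, whereas 9.6.7.2 does not.

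A reader might also infer more than the documents support:
- *About 5% power for any subgroup difference, or no ability to detect one.* This needs an intercept-slope correlation near zero. The documents give no value, and the table shows up to 46%.
- *Any significant modifier would be a chance baseline imbalance.* Leakage can also produce significance. Smoking is classified on trial, so randomization does not guarantee a null level contrast for it.
- *Section 9.6.7.1 contains the same error.* It frames its target as the per-subject rate of change and does not write out a model. It is loosely specified, and no more than that can be said.

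**Conclusion.** The point holds for CIMT and stiffness under the literal reading of 9.6.7.2: the named term tests a time-constant difference in level, not a subgroup difference in the effect on progression. For a 0.012 mm/yr difference it has about 5% power when intercept and slope are uncorrelated and roughly 9-46% at correlations of ±0.3 to ±0.5, against 59-96% for the three-way term.

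These figures rest on the assumed variance components, 60 per cell and complete follow-up. Only gender has a 50% target, and uneven splits would lower power. With 48 per cell (20% loss) the same formulas give 49-91% for the three-way term and at most 38% for the literal one. The structural point does not depend on any of these values.

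Severity is moderate or minor. The analysis is ancillary, cognition is specified correctly, and the primary, co-primary and secondary tests are untouched.

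**What to change.** In 9.6.7.2, state that for CIMT and stiffness the tested term is treatment × time-on-study × modifier, with all lower-order terms including modifier × time. Treatment × modifier in a regression of per-subject slopes is an equivalent alternative. Report the treatment × time estimate with its confidence interval in each subgroup. Keep treatment × subgroup for the cognition change scores.

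In 9.6.7.1, a matching clarification is desirable but secondary: variable × time for the association with rate of change, and variable × time × treatment for its comparison between arms.

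The cost is one sentence in each section, with no new data and no change to the primary models. If the three-way term was always intended, the edit simply records that before unblinding.

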9.6.7.3 Mediators of Treatment Efficacy

We will test the hypothesis that nattokinase treatment-related reductions in atherosclerosis and cognitive measures will be mediated through hemostatic, fibrinolytic and hemorheological factors as well as attenuation of inflammation, monocyte activation, vascular endothelium injury and activation of

vascular endothelium by circulating monocytes. We will use structural equation models to test for mediation. Observed outcome variables will be changes in CIMT (annualized change rate), stiffness (annualized change rate) or cognitive composite scores. For each of the potential mediator that shows a significant treatment effect, we will test the direct effects of randomized treatment and the indirect effects of treatment (i.e., treatment acting through the potential mediators). Bootstrapping will be used to obtain 95% confidence intervals on the direct and indirect effects; confidence intervals that exclude the value of 0 will be considered as evidence for statistical significance.

9.6.7.4 Correlations in Atherosclerosis and Cognitive Outcome Measures

We will use mixed effects models to test the hypothesis that the reduction in subclinical atherosclerosis progression and cognitive decline with nattokinase will be correlated. The dependent variable will be each value of the CIMT (or arterial stiffness) measure at each study time point. The primary independent variables will be the 18-month and 36-month change in cognitive composites. Interaction terms of time on study with the cognitive composite change scores will test whether the rate of change in CIMT (or arterial stiffness) is associated with the change in cognition.

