1.2 Objectives and Hypotheses

The goal of the proposed study is to determine under randomized controlled trial conditions whether nattokinase reduces subclinical atherosclerosis and cognitive decline in healthy women and men. Our hypotheses are: 1) Compared to placebo, nattokinase will show less subclinical atherosclerosis progression and cognitive decline in healthy women and men; 2) The reduction in subclinical atherosclerosis progression and cognitive decline with nattokinase will be correlated; and, 3) The reduction in progression of subclinical atherosclerosis and cognitive decline with nattokinase will be mediated through hemostatic, fibrinolytic and hemorheological factors as well as attenuation of inflammation, monocyte activation, vascular endothelium injury and activation of vascular endothelium by circulating monocytes.

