9.3.2 Study Data

- 1) For each study ultrasound image, the following measures will be obtained:
 - a) Carotid artery IMT, averaged over the distal centimeter of the right common carotid artery far wall (primary trial end point).
 - b) Carotid artery luminal diameter, averaged over the distal centimeter of the right common carotid artery lumen during systole and diastole. Carotid artery diameters will be used in conjunction with pulse pressure to calculate the two measures of arterial stiffness (co-primary trial end points – arterial distensibility and arterial compliance).

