9.6.5.3 Secondary Efficacy Analysis: Cognition Analyses

Three composite cognitive measures will be used to test for randomized treatment group differences in cognition; each composite will be considered as co-secondary endpoints. (1) The global composite will use scores from all neuropsychological tests. (2) The verbal memory composite will use the California Verbal Learning Test and East Boston Memory Test immediate and delayed recall scores. (3) The executive function composite (determined from principal components of prior trial data) will use scores from the Symbol Digit Modalities Test, the Trail Making Test, the Shipley Abstraction scale, Letter-Number Sequencing, and category fluency. The composites will be calculated as the average of component standardized scores weighted by the inverse interest correlation matrix. Absolute values of change from baseline on each cognitive endpoint will be calculated at both post-randomization cognitive follow-ups (18 and 36 months). General estimating equation models will be used to analyze the repeated measures of change in the cognitive endpoints. The primary independent variables will be randomized treatment group; covariates will include the CIMT randomization stratification variable as well as the baseline value of the cognitive endpoint. Differences in cognitive change will be tested by treatment group. Further analyses will test for interactions with test time (18 versus 36 months) to evaluate whether treatment effects (treatment by time interaction) vary by follow-up time.

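### Section 9.6.7.4 would let hypothesis 2 be claimed from a cohort association, because it does not require a treatment effect on either outcome

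*Combined protocol and SAP*

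**What the plan says.** Section 1.2 lists as the second of three hypotheses: "The reduction in subclinical atherosclerosis progression and cognitive decline with nattokinase will be correlated". Section 9.6.7.4 sets out to "test the hypothesis that the reduction in subclinical atherosclerosis progression and cognitive decline with nattokinase will be correlated".

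The model there is a mixed model with CIMT or arterial stiffness at each time point as the outcome. On predictors it says "The primary independent variables will be the 18-month and 36-month change in cognitive composites". On the test it says "Interaction terms of time on study with the cognitive composite change scores will test whether the rate of change in CIMT" (or in stiffness) is associated with cognitive change. It names no treatment term, no estimate by arm and no condition that either outcome must respond to treatment.

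Neighbouring sections do contain such elements:

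- 9.6.5.1 tests the treatment effect on CIMT by "adding a treatment group by time on-study interaction term".
- 9.6.7.1 states: "Analyses will be conducted in the combined sample with a covariate included to control for treatment group". It adds treatment interactions and says experiment-wise error will be controlled in its own analyses.
- 9.6.7.3 tests mediation only for a mediator that itself shows a significant treatment effect.

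Several outcomes could carry the claim. Section 9.3.2 says carotid diameters "will be used in conjunction with pulse pressure to calculate the two measures of arterial stiffness", in addition to CIMT. Section 9.6.5.3 says: "Three composite cognitive measures will be used to test for randomized treatment group differences in cognition; each composite will be considered as co-secondary endpoints".

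**The concern.** The hypothesis is about effects of the product. The test is about people. A significant time by cognitive change term says that participants with faster wall thickening also lost more cognition. Age, blood pressure or other shared risk factors can produce that equally in both arms.

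This is the only analysis given for one of the trial's three hypotheses. A team that followed 9.6.7.4 exactly could report hypothesis 2 as supported although nattokinase changed neither outcome, and no sentence in the plan prevents it.

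**Working it through.** The plan gives no power, effect size or correlation for this analysis, so there is no figure to reproduce. The fault is visible from the text; the arithmetic shows how easily the test responds to a background association.

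**Inputs from the documents.** n = 240 (1.1, 1.3). Eight scans per person: SV, v00 and months 6, 12, 18, 24, 30, 36 (9.3.3). Sonographer CV below 3% (8.3.2); at the 0.75 mm stratification cut-point (4.2), 3% is 0.0225 mm, so a scan error SD of 0.02 mm is consistent with it.

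**Assumed inputs.** 120 per arm, complete data, two-sided 0.05, SD of true CIMT slopes 0.010 mm/year, reliability of cognitive change 0.6, true background correlation r of 0 to 0.3.

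**Step 1: slope reliability.** With SV and v00 both at time 0, scan times in years are 0, 0, 0.5, 1, 1.5, 2, 2.5, 3, and the sum of squares about the mean is 22.75 − 8 × 1.3125² = 8.969. Error variance of a person's slope = 0.02²/8.969 = 0.0000446. Reliability = 0.0001/(0.0001 + 0.0000446) = 0.69.

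**Step 2: observed correlation.** Multiply r by √(0.69 × 0.6) = 0.644. True correlations of 0.1, 0.2, 0.3 become 0.064, 0.129, 0.193.

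**Step 3: rejection rate with an inert product.** In this balanced design the time by covariate coefficient equals the regression of per-person slopes on the covariate, so Fisher's z applies, with mean atanh(observed r) × √237:

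| True r | Mean z | Closed form | Simulated, as written | Simulated, with treatment and treatment × time |
|---|---|---|---|---|
| 0 | 0 | 5% | 5.1% | 5.1% |
| 0.1 | 0.99 | 17% | 17.0% | 16.9% |
| 0.2 | 1.99 | 51% | 51.3% | 51.2% |
| 0.3 | 3.01 | 85% | 85.5% | 85.4% |

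Varying the inputs one at a time gives 13–21%, 36–64% and 67–94% at 0.1, 0.2 and 0.3. If r is placed on observed rather than true values, the rates are 34%, 88% and above 99%.

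**Step 4: how much the drug contributes.** Take a benefit of 0.5 SD in true values on both outcomes and no within-arm association. The observed standardised effects are 0.5 × √0.69 = 0.416 and 0.5 × √0.6 = 0.387. The pooled correlation they induce is 0.25 × 0.416 × 0.387/√[(1 + 0.416²/4)(1 + 0.387²/4)] = 0.039, which is significant in about 9% of trials against 5% with an inert product. With background r of 0.1, 0.2, 0.3 the simulated rates are 34%, 72% and 95%, so a significant result is 1.1 to 2.0 times as likely as with an inert product. After adjustment for arm it is about equally likely (0.94 to 1.02 times).

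**Step 5: a both-outcomes condition (CIMT pair).** Each outcome must show benefit at two-sided 0.05. Inert product, independent outcomes: 0.025² = 0.06% (simulated 0.07–0.21% over the values of r). At 0.5 SD, the noncentralities are 0.416 × √60 = 3.22 and 0.387 × √60 = 3.00, the powers 0.896 and 0.851, and their product 76%. At 0.3 SD, 0.489 × 0.436 = 21% (simulated 21–24%).

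**The case against.** **The treatment term makes no difference.** Correct: Step 3 shows the inert-product rates hardly move when it is added. Adjustment also removes the drug's own contribution. A reader might infer that the absent treatment term is the main fault and that adding it, or a treatment by time by cognitive change term, repairs the test. It does not. The first leaves a background association. The second asks only whether the association differs by arm, and rejects about 5% of the time even when the drug helps everyone equally on both outcomes.

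**Section 9.6.7.1 may already cover this.** It refers to on-trial endpoint variables as predictors, its list is partly open-ended, and 9.6.7.4 names only the primary independent variables. This is a fair reading, but cognition is not among the listed predictors and 9.6.7.4 does not refer back. Even if imported, 9.6.7.1 requires no treatment effect. Its experiment-wise error sentence does matter: the documents do not support saying that multiplicity is ignored, only that it is unclear whether that control reaches 9.6.7.4.

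**The wording already limits the claim.** Hypothesis 2 presupposes a reduction due to nattokinase, and the 9.6.5 tests would show whether there is one. A careful author would not claim it after null efficacy results. That lowers the risk, but 9.6.7.4 presents its one test as the test of the hypothesis and states no such condition.

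**The figures depend on the assumed correlation.** This stands. They show that a background association is readily detected at n=240, not that one exists or that the trial is likely to mislead.

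**Conclusion.** The point holds as a fault in how hypothesis 2 is to be decided: the stated test measures a cohort association, and no treatment benefit on either outcome is needed to claim a treatment-specific result. This follows from the text and needs no simulation. The rates in the working apply to CIMT and rest on the assumed slope SD, reliability and correlation; no stiffness-specific calculation was made.

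Two stronger readings are not supported. The result would not be wholly unrelated to nattokinase, since a benefit on both outcomes raises the unadjusted term somewhat; the two sources just cannot be told apart. Nor is the trial's efficacy evidence affected: this analysis is ancillary and the 9.6.5 tests stand on their own. The change should be made because the section is the only test of a stated hypothesis.

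**What to change.** In section 9.6.7.4:

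1. State that hypothesis 2 will be claimed only for a pre-named pair (CIMT, distensibility or compliance, with the global, verbal memory or executive composite) in which both outcomes show a treatment benefit in the 9.6.5 analyses. Say that this is necessary but not sufficient. It parallels the condition already in 9.6.7.3.
2. Otherwise report the time by cognitive change result as a descriptive cohort association, adjusted for treatment and treatment by time and also by arm, with confidence intervals.
3. Cross-refer to 9.6.7.1 and say whether its experiment-wise error control covers the 3 × 3 = 9 possible pairs.

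The cost is SAP wording, two model terms and arm-specific estimates; no new data are needed. The downside is that hypothesis 2 may end inconclusive: for a CIMT pair the condition is met in about 75% of simulated trials at a 0.5 SD benefit on both outcomes, and about 20–24% at 0.3 SD. Arm-specific estimates are also imprecise: the 95% interval for a correlation near zero is about ±1.96/√117 = ±0.18 with 120 per arm, against ±1.96/√237 = ±0.13 pooled.
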